7.2. STATISTICAL ANALYSIS

See sections 2~5.

7.2.1. Safety Analysis

See sections 2~5.

7.2.2. Analysis of Efficacy Analysis

See sections 2~5.

PFIZER CONFIDENTIAL

Page 21 of 56

7.2.3. Summary of Analyses

Efficacy and safety analyses excluding descriptive summaries will be shown in the following table.

1) Unbalanced cohorts

Outcome	Analysis Set	Supports Protocol Objective Number	Subgroups	Statistical Method	Covariates/ Strata	Missing Data
The incidence rates of stroke/SE and major bleeding per 1,000 person-years	Unbalanced patients With high bleeding risk cohort vs without high bleeding risk cohort	NA	NA	1000 person-years (no statistical comparison)	Refer to 5.4	No imputation
Interaction analysis	Unbalanced patients With high bleeding risk cohort vs without high bleeding risk cohort	NA	NA	Cox proportional hazards model	With/without high bleeding risk, Warfarin/apixaban	No imputation

2) Balanced cohorts

Outcome	Analysis Set	Supports Protocol Objective Number	Subgroups	Statistical Method	Covariates/ Strata	Missing Data
Major bleeding	Balanced patients Warfarin vs. apixaban Cohorts	safety, primary	Whole cohort, primary analysis	Cox proportional hazards model	Refer to 5.4	No imputation
Major bleeding	Balanced patients Warfarin vs. apixaban Cohorts	safety, primary	Whole cohort, primary analysis	Plot of Kaplan-Meier Estimates		No imputation
Major bleeding	Balanced patients Warfarin vs. apixaban Cohorts	safety, primary	Whole cohort, primary analysis	Incidence rate (per 1000 patient-year)		No imputation
Major intracranial bleeding	Balanced patients Warfarin vs. apixaban Cohorts	Safety Secondary	Whole cohort, secondary analysis	Cox proportional hazards model	Refer to 5.4	No imputation
Major intracranial bleeding	Balanced patients Warfarin vs. apixaban Cohorts	Safety Secondary	Whole cohort, secondary analysis	Plot of Kaplan-Meier Estimates		No imputation
Major intracranial bleeding	Balanced patients Warfarin vs. apixaban Cohorts	Safety Secondary	Whole cohort, secondary analysis	Incidence rate (per 1000 patient-year)		No imputation
Major GI bleeding	Balanced patients Warfarin vs. apixaban Cohorts	Safety Secondary	Whole cohort, secondary analysis	Cox proportional hazards model	Refer to 5.4	No imputation
Major GI bleeding	Balanced patients Warfarin vs. apixaban Cohorts	Safety Secondary	Whole cohort, secondary analysis	Plot of Kaplan-Meier Estimates		No imputation
Major GI bleeding	Balanced patients Warfarin vs. apixaban Cohorts	Safety Secondary	Whole cohort, secondary analysis	Incidence rate (per 1000 patient-year)		No imputation

PFIZER CONFIDENTIAL

Page 22 of 56

Outcome	Analysis Set	Supports Protocol Objective Number	Subgroups	Statistical Method	Covariates/ Strata	Missing Data
Stroke/SE	Balanced patients	Effectiveness	Whole cohort, secondary	Cox proportional	Refer to 5.4	No
	Warfarin vs. apixaban Cohorts	Primary Effectiveness	analysis Whole cohort, secondary	hazards model		imputation No
Stroke/SE	Balanced patients Warfarin vs. apixaban Cohorts	Primary	analysis	Plot of Kaplan-Meier Estimates		
	Balanced patients	Effectiveness	Whole cohort, secondary	Incidence rate (per 1000		imputation No
Stroke/SE	Warfarin vs. apixaban Cohorts	Primary	analysis	patient-year)		imputation
Stroke	Balanced patients Warfarin vs. apixaban Cohorts	Effectiveness Secondary	Whole cohort, secondary analysis	Cox proportional hazards model	Refer to 5.4	No imputation
	Balanced patients	Effectiveness	Whole cohort, secondary	Plot of Kaplan-Meier		No
Stroke	Warfarin vs. apixaban Cohorts	Secondary	analysis	Estimates		imputation
Stroke	Balanced patients	Effectiveness	Whole cohort, secondary	Incidence rate (per 1000		No
	Warfarin vs. apixaban Cohorts	Secondary	analysis	patient-year)		imputation
SE	Balanced patients Warfarin vs. apixaban Cohorts	Effectiveness Secondary	Whole cohort, secondary analysis	Cox proportional hazards model	Refer to 5.4	No imputation
SE	Balanced patients	Effectiveness	Whole cohort, secondary	Plot of Kaplan-Meier		No
	Warfarin vs. apixaban Cohorts	Secondary	analysis	Estimates		imputation
SE	Balanced patients Warfarin vs. apixaban Cohorts	Effectiveness Secondary	Whole cohort, secondary analysis	Incidence rate (per 1000 patient-year)		No imputation
Safety: Major Bleeding	Balanced patients	Safety/effectiveness	Hypertension subgroup,			No
Effectiveness: stroke/SE	Warfarin vs. apixaban Cohorts	Exploratory	exploratory analysis	1000 person-years	Refer to 5.4	imputation
Safety: Major Bleeding	Balanced patients	Safety/effectiveness	Hypertension subgroup,	Incidence rate (per 100 patient-year) (no		No
Effectiveness: stroke/SE	Warfarin vs. apixaban Cohorts	Exploratory	exploratory analysis	statistical comparison)		imputation
Safety: Major Bleeding	Balanced patients	Safety/effectiveness	Hypertension subgroup,	Plot of Kaplan-Meier		No
Effectiveness: stroke/SE	Warfarin vs. apixaban Cohorts	Exploratory	exploratory analysis	Estimates		imputation
Safety: Major Bleeding Effectiveness: stroke/SE	Balanced patients Warfarin vs. apixaban Cohorts	Safety/effectiveness Exploratory	Liver dysfunction subgroup, exprolatory analysis	1000 person-years	Refer to 5.4	No imputation
Safety: Major Bleeding Effectiveness: stroke/SE	Balanced patients Warfarin vs. apixaban Cohorts	Safety/effectiveness Exploratory	Liver dysfunction subgroup, exprolatory analysis	Incidence rate (per 100 patient-year) (no statistical comparison)		No imputation
Safety: Major Bleeding Effectiveness: stroke/SE	Balanced patients Warfarin vs. apixaban Cohorts	Safety/effectiveness Exploratory	Liver dysfunction subgroup, exprolatory analysis	Plot of Kaplan-Meier Estimates		No imputation
Safety: Major Bleeding Effectiveness: stroke/SE	Balanced patients Warfarin vs. apixaban Cohorts	Safety/effectiveness Exploratory	Renal impairment, exploratory analysis	1000 person-years	Refer to 5.4	No imputation
Safety: Major Bleeding	Balanced patients	Safety/effectiveness	Renal impairment,	Incidence rate (per 100		No
Effectiveness: stroke/SE	Warfarin vs. apixaban Cohorts	Exploratory	exploratory analysis	patient-year)		imputation

Page 23 of 56

Outcome	Analysis Set	Supports Protocol Objective Number	Subgroups	Statistical Method	Covariates/ Strata	Missing Data
				(no statistical comparison)		
Safety: Major Bleeding Effectiveness: stroke/SE	Balanced patients Warfarin vs. apixaban Cohorts	Safety/effectiveness Exploratory	Renal impairment Renal impairment, exprolatory analysis	Plot of Kaplan-Meier Estimates		No imputation
Safety: Major Bleeding Effectiveness: stroke/SE	Balanced patients Warfarin vs. apixaban Cohorts	Safety/effectiveness Exploratory	Bleeding history subgroup, exploratory analysis	1000 person-years	Refer to 5.4	No imputation
Safety: Major Bleeding Effectiveness: stroke/SE	Balanced patients Warfarin vs. apixaban Cohorts	Safety/effectiveness Exploratory	Bleeding history subgroup, exploratory analysis	Incidence rate (per 100 patient-year) (no statistical comparison)		No imputation
Safety: Major Bleeding Effectiveness: stroke/SE	Balanced patients Warfarin vs. apixaban Cohorts	Safety/effectiveness Exploratory	Bleeding history subgroup, exploratory analysis	Plot of Kaplan-Meier Estimates		No imputation
Safety: Major Bleeding Effectiveness: stroke/SE	Balanced patients Warfarin vs. apixaban Cohorts	Safety/effectiveness Exploratory	Concomitant use of antiplatelet drug, exploratory analysis	1000 person-years	Refer to 5.4	No imputation
Safety: Major Bleeding Effectiveness: stroke/SE	Balanced patients Warfarin vs. apixaban Cohorts	Safety/effectiveness Exploratory	Concomitant use of antiplatelet drug, exploratory analysis	Incidence rate (per 100 patient-year) (no statistical comparison)		No imputation
Safety: Major Bleeding Effectiveness: stroke/SE	Balanced patients Warfarin vs. apixaban Cohorts	Safety/effectiveness Exploratory	Concomitant use of antiplatelet drug, exploratory analysis	Plot of Kaplan-Meier Estimates		No imputation
Safety: Major Bleeding Effectiveness: stroke/SE	Balanced patients Warfarin vs. apixaban Cohorts	Safety/effectiveness Exploratory	Age ✓ >80 y ✓ >90 y exploratory analysis	1000 person-years	Refer to 5.4	No imputation
Safety: Major Bleeding Effectiveness: stroke/SE	Balanced patients Warfarin vs. apixaban Cohorts	Safety/effectiveness Exploratory	Age ✓ >80 y ✓ >90 y exploratory analysis	Incidence rate (per 100 patient-year) (no statistical comparison)		No imputation
Safety: Major Bleeding Effectiveness: stroke/SE	Balanced patients Warfarin vs. apixaban Cohorts	Safety/effectiveness Exploratory	Age ✓ >80 y ✓ >90 y exploratory analysis	Plot of Kaplan-Meier Estimates		No imputation
Safety: Major Bleeding Effectiveness: stroke/SE	Balanced patients Warfarin vs. apixaban Cohorts	Safety/effectiveness Exploratory	Peptic ulcer, exploratory analysis	1000 person-years	Refer to 5.4	No imputation

Outcome	Analysis Set	Supports Protocol Objective Number	Subgroups	Statistical Method	Covariates/ Strata	Missing Data
Safety: Major Bleeding Effectiveness: stroke/SE	Balanced patients Warfarin vs. apixaban Cohorts	Safety/effectiveness Exploratory	Peptic ulcer, exploratory analysis	Incidence rate (per 100 patient-year) (no statistical comparison)		No imputation
Safety: Major Bleeding Effectiveness: stroke/SE	Balanced patients Warfarin vs. apixaban Cohorts	Safety/effectiveness Exploratory	Peptic ulcer, exploratory analysis	Plot of Kaplan-Meier Estimates		No imputation
Safety: Major Bleeding Effectiveness: stroke/SE	Balanced patients Warfarin vs. apixaban Cohorts	Safety/effectiveness Exploratory	Active cancer, exploratory analysis	1000 person-years	Refer to 5.4	No imputation
Safety: Major Bleeding Effectiveness: stroke/SE	Balanced patients Warfarin vs. apixaban Cohorts	Safety/effectiveness Exploratory	Active cancer, exploratory analysis	Incidence rate (per 100 patient-year) (no statistical comparison)		No imputation
Safety: Major Bleeding Effectiveness: stroke/SE	Balanced patients Warfarin vs. apixaban Cohorts	Safety/effectiveness Exploratory	Active cancer, exploratory analysis	Plot of Kaplan-Meier Estimates		No imputation
Safety: Major Bleeding Effectiveness: stroke/SE	Balanced patients Warfarin vs. apixaban Cohorts	Safety/effectiveness Exploratory	Low body weight, exploratory analysis	1000 person-years	Refer to 5.4	No imputation
Safety: Major Bleeding Effectiveness: stroke/SE	Balanced patients Warfarin vs. apixaban Cohorts	Safety/effectiveness Exploratory	Low body weight, exploratory analysis	Incidence rate (per 100 patient-year) (no statistical comparison)		No imputation
Safety: Major Bleeding Effectiveness: stroke/SE	Balanced patients Warfarin vs. apixaban Cohorts	Safety/effectiveness Exploratory	Low body weight, exploratory analysis	Plot of Kaplan-Meier Estimates		No imputation
Safety: Major Bleeding Effectiveness: stroke/SE	Balanced patients Warfarin vs. apixaban Cohorts	Safety/effectiveness Exploratory	Diabetes mellitus, exploratory analysis	1000 person-years	Refer to 5.4	No imputation
Safety: Major Bleeding Effectiveness: stroke/SE	Balanced patients Warfarin vs. apixaban Cohorts	Safety/effectiveness Exploratory	Diabetes mellitus, exploratory analysis	Incidence rate (per 100 patient-year) (no statistical comparison)		No imputation
Safety: Major Bleeding Effectiveness: stroke/SE	Balanced patients Warfarin vs. apixaban Cohorts	Safety/effectiveness Exploratory	Diabetes mellitus, exploratory analysis	Plot of Kaplan-Meier Estimates		No imputation
Safety: Major Bleeding Effectiveness: stroke/SE	Balanced patients Warfarin vs. apixaban Cohorts	Safety/effectiveness Exploratory	Polypharmacy, exploratory analysis	1000 person-years	Refer to 5.4	No imputation
Safety: Major Bleeding Effectiveness: stroke/SE	Balanced patients Warfarin vs. apixaban Cohorts	Safety/effectiveness Exploratory	Polypharmacy, exploratory analysis	Incidence rate (per 100 patient-year) (no statistical comparison)		No imputation
Safety: Major Bleeding Effectiveness: stroke/SE	Balanced patients Warfarin vs. apixaban Cohorts	Safety/effectiveness Exploratory	Polypharmacy, exploratory analysis	Plot of Kaplan-Meier Estimates		No imputation

Page 25 of 56

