First, all patients with NVAF who are newly diagnosed and initiated apixaban or warfarin will be extracted from the database. Among these patients, patients with at least one predetermined high bleeding risks will be extracted. In this study, predetermined high bleeding risks are 1) patients with hypertension diagnosis, 2) patients with liver dysfunction, 3) patients with renal dysfunction diagnosis, 4) patients with a history of bleeding, 5) patients with hemorrhagic stroke, 6) patients with alcohol abuse, 7) patients with concomitant used of antiplatelet drugs, 8) patients with chronic (continuously for longer than 90 days) concomitant use of Non-steroidal antiinflammatory drug (NSAID), 9) highly elderly (> 80 years old), 10) patients with refractory hypertension, 11) patients with a history of peptic ulcer diagnosis, 12) patients with active cancer, 13) patients with diabetes mellitus, 14) patients whose body weight is <40kg, 15) patients with polypharmacy (sea Section 5.4 for the definition). Patients with at least one predetermined high bleeding risk factor will be divided into two cohorts, apixaban and warfarin cohorts, based on the first prescribed drug just after the NVAF diagnosis. Patient characteristics will be balanced by using an inverse probability of treatment weighting (IPTW) method to create balanced apixaban and balanced warfarin cohorts. Comparisons will be conducted by using these balanced warfarin and apixaban cohorts (Kaplan-meier curves, incidence rates per 1,000 person-year and hazard ratio with 95% confident intervals). The primary safety and effectiveness analyses are comparison of apixaban with warfarin in patients with at least one predetermined risk factor for bleeding.

- Second, after the first analysis, we will conduct separate interaction analysis of the treatment (apixaban vs. warfarin) and one of the 15 risk factors (e.g., hypertension yes vs no, etc) to see if treatment effects are consistent among patients with or without each specific factor
- Third, patients will be stratified by risk factors into 15 subgroups, and same IPTW analyses as described in the step 1 will be conducted only in the subgroups with adequate sample sizes.

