7. STATISTICAL METHODOLOGY AND STATISTICAL ANALYSES

7.1. STATISTICAL METHODS

7.1.1. Calculation of Propensity Score

In this study, balanced cohorts (apixaban vs. warfarin) will be created by an IPTW method. Propensity scores will be estimated by unconditional logistic regression analyses that incorporate potential predictors of therapy as independent variables in the regression and cohort status as the outcome. Using calculated propensity score an IPTW method will be applied to balance the warfarin and apixaban cohorts, which will be used for the comparisons of all endpoints (sections 5.1 and 5.2). The following covariates will be included in the logistic regression for calculation of propensity score:

• age on index date

- gender
- CHADS2 score in baseline
- CHA2DS2-VASc score in baseline
- heart failure diagnosis in baseline
- coronary heart disease diagnosis in baseline
- peripheral arterial disorder diagnosis in baseline
- myocardial infarction diagnosis in baseline
- hyperthyroidism or thyrotoxicosis in baseline
- TIA diagnosis in baseline
- stroke or SE diagnosis in baseline
- renal dysfunction diagnosis in baseline
- liver dysfunction diagnosis in baseline
- bleeding diagnosis in baseline
- hypertension diagnosis in baseline
- diabetes mellitus diagnosis in baseline
- treated with antiplatelet drug in baseline
- treated with NSAIDs in baseline
- treated with gastric secretion inhibitor in baseline
- treated with statin-based drug in baseline
- treated with anti-hypertensives in baseline
- treated with anti-arrhythmics in baseline
- treated with beta-blockers in baseline
- treated with heparins in baseline
- cardioversion in baseline

The operational definitions for the above covariates are shown in the Section 5.4.

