7.1.6. Cox proportional hazards model

Cox proportional hazards model will be used to compare endpoints (time-to-endpoint) in the propensity-score-weighted cohorts with robust sandwich estimates to account for the potential clustering within weighted sets. The Cox proportional hazards model will include only index OAC treatment as the independent variable if patient characteristics are balanced between groups... If not balanced, the unbalanced variable will be also included to the model in addition to the index OAC PFIZER CONFIDENTIAL

treatment. The hazard ratios with corresponding 95% confidence intervals and p-values will be reported.

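### SAP 2.1 plans a treatment interaction for each of 15 bleeding risk factors, but the only interaction row in SAP 7.2.3 is an unweighted Cox model of any-high-risk status

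*SAP*

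**What the plan says.** SAP 2.1 sets out three steps. Step 1 begins with the whole initiator population ("First, all patients with NVAF who are newly diagnosed and initiated apixaban or warfarin will be extracted from the database"), then selects patients with at least one of 15 listed risk factors and balances the two drug cohorts by IPTW. In step 2, "we will conduct separate interaction analysis of the treatment (apixaban vs. warfarin) and one of the 15 risk factors", with hypertension yes or no as the example; the aim is to see whether the treatment effect is consistent with and without each factor. Step 3 repeats the IPTW analysis in subgroups that are large enough. SAP 2.2.4 confirms that the interaction analyses come before the subgroups.

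SAP 7.2.3 introduces its table with "Efficacy and safety analyses excluding descriptive summaries will be shown in the following table". The only interaction row is in the part for unbalanced cohorts. Its analysis set is "Unbalanced patients With high bleeding risk cohort vs without high bleeding risk cohort", its method is a Cox model and its terms are "With/without high bleeding risk, Warfarin/apixaban". It names no outcome, and its protocol objective is given as not applicable. The part for balanced cohorts has no interaction row.

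Elsewhere the SAP works with weighted cohorts. According to 7.1.1 the balanced cohorts are those "which will be used for the comparisons of all endpoints (sections 5.1 and 5.2"), and 7.1.6 fits the Cox model "in the propensity-score-weighted cohorts with robust sandwich estimates".

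**The concern.** A programmer working from 7.2.3 would fit one crude model of any risk against no risk. A programmer working from 2.1 would fit 15 factor-specific models and would have to guess the population, weighting and outcome. Section 7.1.7 does not settle this, because it gives subgroup hazard ratios but no interaction term. Sections 7.2.1 and 7.2.2 only refer back to sections 2 to 5.

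The weighting matters because Protocol 9.9 concedes that patients on the two drugs may not be comparable. In an unweighted interaction model, confounding that differs between strata can look like effect modification, or can hide it. The results would also be read as evidence. SAP 3.2 keeps p<0.05 as the mark of significance for exploratory subgroup analyses, and SAP 7.1.9 itself uses interaction p-values from the phase 3 trial to argue that the hazard ratio is stable across subgroups.

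**Working it through.** **1. Count.** SAP 2.1 lists 15 risk factors, which agrees with its stated 15. The table in 7.2.3 has 1 interaction row and 0 factor-specific interaction rows.

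**2. Side by side.**

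| Item | 2.1 step 2 | Interaction row in 7.2.3 |
|---|---|---|
| Factor | each of 15, separately | any high risk, yes or no |
| Population | not stated | includes patients with no risk factor, who are outside the 2.1.1 study population although step 1 first extracts them |
| Weighting | not stated | unbalanced |
| Outcome | not stated | not stated |

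Only the first line is a direct contradiction. The SAP never writes the word unweighted. It follows from 2.1, where balanced cohorts are those produced by IPTW.

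**3. What the crude row estimates.** Let B1 and B0 be the factors by which confounding multiplies the hazard ratio in the two strata. Then

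crude ratio of HRs = true ratio x B1/B0,

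which is unbiased only if B1 = B0.

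**4. Illustration (assumed, not from the documents).** Take a true HR of 0.70 in both strata and a binary confounder in one stratum only. For rare events B = (1 + pA(RR-1)) / (1 + pW(RR-1)), with prevalence pA on apixaban and pW on warfarin.

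- RR 1.5, 30% vs 40%: B = 1.15/1.20 = 0.958. The crude HR is 0.70 x 0.958 = 0.67, and the ratio of HRs is 0.96 instead of 1.00.
- RR 2, 30% vs 50%: B = 1.3/1.5 = 0.867. The crude HR is 0.61 and the ratio is 0.87.
- Same confounder in both strata: the ratio is 1.00 and there is no distortion.
- Stronger confounder in one stratum, milder in the other: 0.8667/0.9583 = 0.904.

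**5. Effect on a nominal 5% test (illustrative).** Inputs are the planning rates in SAP 7.1.9, 10,000 patients per arm (the feasibility check found more than this) and an assumed mean follow-up of 1 year.

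- Major bleeding: 10,000 x (0.0377 + 0.0250) = 627 events.
- Stroke/SE: 10,000 x (0.0277 + 0.0179) = 456 events.

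The formulas are SE = sqrt(4/E1 + 4/E0), d = ln(ratio)/SE and rejection = Phi(-1.96-d) + 1 - Phi(1.96-d).

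- *Row as one any-risk contrast*, with the no-risk stratum assumed to hold 5% to 10% of all events (E0 = 33 to 70 for bleeding, 24 to 51 for stroke/SE). SE is 0.357 to 0.253 and 0.419 to 0.296. Rejection is 5.2% to 8.8% for bleeding and 5.1% to 7.7% for stroke/SE.
- *Row applied factor by factor*, with the factor assumed present in 10% to 50% of at-risk events. SE is 0.266 to 0.160 and 0.312 to 0.187. Rejection is 5.3% to 14.6% and 5.2% to 11.9% per factor. For the largest value, d = ln(0.867)/0.160 = -0.90, which gives 14.6%.

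Each range runs from the weaker confounder with the largest SE to the stronger confounder with the smallest. The results depend heavily on the assumptions. With mean follow-up of 0.5 to 2 years, the 14.6% becomes 9.7% to 24.5%. With the milder confounder also present in the other stratum (ratio 0.904), the bleeding maxima fall to 6.8% and 9.6%.

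**The case against.** The best defence is that the row is not step 2 at all. It sits under an explicit heading for unbalanced cohorts, beside crude rates for the same two groups, and supports no protocol objective. IPTW weights are planned only for patients with at least one risk factor, so none exist for the no-risk stratum. Step 2 itself lies between an IPTW step and another IPTW step, and nowhere says that its own models are crude. On this view the row is a deliberate crude description and step 2 merely lacks a row.

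Much of this stands. A reader might infer that the SAP plans the 15 factor-specific interactions without weighting. The documents do not support that, because step 2 leaves weighting open. A reader might also infer that step 2 has been dropped because the table is exhaustive. The introductory sentence does not claim to cover every analysis, the table includes purely descriptive rates, and it also omits the subgroup Cox models that 7.1.7 plans. The missing row is therefore a gap in the table and no proof of intent.

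The alternative defence, that the row is shorthand for each factor in turn, fits poorly. Its analysis set names a high-risk cohort against a cohort without high risk, and where 7.2.3 means single factors it names them one by one.

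The defence does not explain why a Cox interaction model, as opposed to a table of rates, should be crude when 7.1.1 and 7.1.6 put endpoint comparisons in weighted cohorts. Nor does it tell the programmer how to run step 2.

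**Conclusion.** The mismatch is certain: 15 single-factor interactions in 2.1 against one composite interaction in 7.2.3, with the outcome stated in neither. That the row as written is open to differential confounding follows from its unweighted design. That this reaches the step 2 consistency check is conditional on the row being used to implement step 2.

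The size of the distortion is unknown. The ratios of 0.96 and 0.87 and all the rejection rates rest on an invented confounder, assumed event shares and assumed follow-up. They show that distortion is possible and should not be read as an estimate of the study's false-positive rate.

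The consequence is limited. The analyses are exploratory, subgroups are chosen on sample size (2.2.4), no definitive subgroup conclusions are planned (3.2, 7.1.7), and the primary IPTW comparisons are unaffected. The point should be corrected before analysis, since the correction is cheap and uses methods the SAP already contains.

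**What to change.** - Reconcile 2.1 step 2 with 7.2.3 on factor, population, weighting and outcome.
- List the interaction analysis under balanced cohorts: one IPTW-weighted Cox model with robust variance per factor and primary outcome, with terms for treatment, factor and treatment x factor. That is 15 x 2 = 30 models. SAP 2.2.4 says only that four small factors might be left out of the further subgroup analysis. Dropping them from step 2 as well (11 x 2 = 22 models) requires 2.1 to be amended.
- Apply the existing 10% standardized-difference check (7.1.2) within each factor level, and add unbalanced variables as 7.1.6 already provides. This matters most for factors with no term of their own in the 7.1.1 propensity list ("The following covariates will be included in the logistic regression for calculation of propensity score"), such as peptic ulcer, cancer, body weight below 40 kg and polypharmacy.
- If the at-least-one-risk population is used, state that every factor-absent patient carries some other risk factor.
- Keep the any-risk against no-risk contrast as descriptive rates only, or weight it and define it as a separate analysis in all NVAF initiators.

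Cost: a table edit and some programming. In the at-least-one-risk population the step 1 weights can be reused; a weighted any-risk contrast needs one more propensity model. Intervals for the exploratory terms will be somewhat wider.
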